C _{tau}	trough concentration
CTCAE	Common Terminology Criteria for Adverse Events
CYP	cytochrome P450
DLI	donor lymphocyte infusion
DLT	dose-limiting toxicity
DMC	Data Monitoring Committee
DNA	deoxyribonucleic acid
DoR	duration of response
EBV	Epstein-Barr virus
ECG	electrocardiogram

Abbreviations and Special Terms	Definition
eCRF	electronic case report form
EDC	electronic data capture
EOT	end of treatment
EQ-5D-3L	EuroQol EQ-5D 3 level version
FDA	Food and Drug Administration
FEV1%	forced expiratory volume in 1 second as a percentage of predicted
GCP	Good Clinical Practice
GI	gastrointestinal
GVHD	graft-versus-host disease
НВс	hepatitis B core
HBsAg	hepatitis B surface antigen
HBV	hepatitis B virus
HCV	hepatitis C virus
HIPAA	Health Insurance Portability and Accountability Act of 1996
HIV	human immunodeficiency virus
HLA	human leukocyte antigen
IB	Investigator's Brochure
ICF	informed consent form
ICH	International Council on Harmonization of Technical Requirements for Registration of Pharmaceuticals for Human Use
IEC	independent ethics committee
IFN	interferon
IL	interleukin
IRB	institutional review board
ITT	intent-to-treat
IV	intravenous
IVRS	interactive voice response system
JAK	Janus kinase
ka	absorption rate
KPS	Karnofsky Performance Status
LFT	liver chemistry test
LSS	Lee Chronic Graft-Versus-Host Disease Symptom Scale
MDS	myelodysplastic syndrome
MedDRA	Medical Dictionary for Regulatory Activities
MPN	myeloproliferative neoplasm
MR	malignancy relapse
NCI	National Cancer Institute
NIH	National Institute of Health

Abbreviations and		
Special Terms	Definition	
NHL	non-Hodgkin lymphoma	
NRM	nonrelapse mortality	
OMRS	Oral Mucosa Rating Scale	
ORR	overall response rate	
OS	overall survival	
PBPK	physiologically based pharmacokinetic	
PCR	polymerase chain reaction	
PD	progressive disease	
PFT	pulmonary function test	
PGIC	Patient Global Impression of Change	
PGIS	Patient Global Impression of Severity	
PK	pharmacokinetic	
PML	progressive multifocal leukoencephalopathy	
PO	orally	
PR	partial response	
QD	once daily	
QOD	every other day	
QOL-SF-36 v2	Quality-of-Life Questionnaire 36-Item Short Form Survey version 2	
RAEB	refractory anemia with excess blasts	
RNA	ribonucleic acid	
RSI	Reference Safety Information	
SAE	serious adverse event	
SOP	standard operating procedure	
SUSAR	suspected unexpected serious adverse reaction	
STAT	signal transducer and activator of transcription	
TEAE	treatment-emergent adverse event, AEs reported for the first time or worsening of a pre-existing event after first dose of study treatment	
T_{max}	time to maximum concentration	
TNF	tumor necrosis factor	
TYK	tyrosine kinase	
ULN	upper limit of normal	
V/F	volume of distribution after oral administration	

1. PROTOCOL SUMMARY

Protocol Title: GRAVITAS-309: A Phase 2/3 Study of Itacitinib and Corticosteroids as Initial

Treatment for Chronic Graft-Versus-Host Disease

Protocol Number: INCB 39110-309

Objectives and Endpoints: Table 1 and Table 2 present the objectives and endpoints in

Parts 1/1 expansion and 2, respectively.

Table 1: Objectives and Endpoints, Part 1 and Part 1 Expansion

Objectives	Endpoints
Primary	
To identify an appropriate dose of itacitinib in combination with corticosteroids as initial treatment for moderate or severe cGVHD.	Part 1: DLT data through Day 28 and additional data from clinical safety and laboratory assessments. Part 1 expansion: Incidence and severity of adverse events, across treatment cohorts.
Key Secondary (for Part 1 Expansion)	
To evaluate preliminary activity across treatment cohorts with respect to response rate at Month 3 and Month 6.	Response rate at Month 3 and Month 6, defined as the proportion of participants who demonstrate a CR or PR at each timepoint.
Secondary	
To evaluate the PK of itacitinib when administered in combination with corticosteroids in the study population.	C _{max} , C _{min} , T _{max} , AUC _{0-t} , and Cl/F.
To estimate efficacy outcomes for each treatment cohort.	Part 1: Response rate at Month 3, 6, and 12. Part 1 expansion: Response rate at Month 12. Response rate is defined as the proportion of participants who demonstrate either a CR or PR at each timepoint.
	Time to response, defined as the interval between randomization and first response.
	DoR, defined as the interval between first response and cGVHD progression, death, or initiation of new systemic cGVHD therapy.
	OS, defined as the interval between the date of randomization and the date of death due to any cause.
	NRM, defined as the proportion of participants who died due to causes other than a relapse of their primary hematologic disease.
	Proportion of participants with $\geq 50\%$ reduction in daily corticosteroid dose at Day 180.
	Proportion of participants successfully tapered off all corticosteroids at Day 180.
	Relapse rate of malignant and nonmalignant hematologic diseases, defined as the proportion of participants whose underlying disease relapses.
	Time to primary hematologic disease relapse, defined as the interval between the date of randomization and the date of relapse.

Table 2: Objectives and Endpoints, Part 2

Objectives	Endpoints
Primary	
To compare the efficacy of itacitinib versus placebo in combination with corticosteroids as initial treatment for moderate or severe cGVHD.	Response rate at Month 6, defined as the proportion of participants demonstrating a CR or PR at Month 6.
Secondary	
To compare changes in health-related quality of life.	Changes in symptom scores using the LSS, QOL-SF-36 v2, EQ-5D-3L, PGIC, and PGIS.
To compare additional efficacy outcomes between treatment groups.	Response rate at Month 3 and 12, defined as the proportion of participants who demonstrate either a CR or PR at each timepoint.
	DoR, defined as the interval between first response and cGVHD progression, death, or initiation of new systemic cGVHD therapy.
	OS, defined as the interval between the date of randomization and the date of death due to any cause.
	NRM, defined as the proportion of participants who died due to causes other than a relapse of their primary hematologic disease.
	Proportion of participants with $\geq 50\%$ reduction in daily corticosteroid dose at Day 180.
	Proportion of participants successfully tapered off all corticosteroids at Day 180.
	Relapse rate of malignant and nonmalignant hematologic diseases, defined as the proportion of participants whose underlying disease relapses.
	Time to primary hematologic disease relapse, defined as the interval between the date of randomization and the date of relapse.
To evaluate the PK of itacitinib in combination with corticosteroids in 1L cGVHD.	C _{min} in all participants; C _{max} , T _{max} , AUC _{0-t} , and Cl/F, data permitting.
To evaluate the safety and tolerability of study treatment across the 2 treatment cohorts.	Data from clinical safety assessments (eg, AEs, infections) will be listed and tabulated.

Overall Design:

Table 3 presents the key study design elements.

Table 3: Key Study Design Elements

Study Phase	Phase 2/3
Clinical Indication	Chronic graft-versus-host disease
Population	Males and females who are at least 18 years of age who have not previously received systemic treatment for moderate or severe cGVHD.
Number of Participants	Approximately 401 participants will be enrolled in this study. In Part 1, approximately 20 participants will be randomized 1:1 to 1 of 2 treatment groups (10 participants per group). In Part 1 expansion, approximately 140 patients will be randomized 1:1 to 1 of 4 treatment groups (35 participants per group, including those from Part 1 meeting the criteria).
	In Part 2, approximately 246 participants will be randomized 1:1 to 1 of 2 treatment groups (123 participants per group).
Study Design	Part 1 and Part 1 expansion: randomized, open-label Part 2: randomized, double-blind, placebo-controlled
Estimated Duration of Study Participation	 It is estimated that an individual participant may participate for as long as 38 months, which includes the following: up to 28 days for screening. continuous treatment until treatment withdrawal criteria are met or for a maximum of 36 months. a minimum of 30 days for safety follow-up. post-treatment cGVHD follow-up for participants who completed itacitinib/placebo taper after initial response (CR or PR) or discontinued early for reasons other than cGVHD progression and with no requirement for new systemic cGVHD therapy (for a maximum of 24 months from Day 1). participants will be followed for survival until the participant dies or withdraws consent.

Treatment Groups and Duration:

Part 1 is a run-in that will employ a randomized, open-label, parallel-cohort design to assess the safety and tolerability of itacitinib in combination with corticosteroids (Figure 1). A total of 20 participants with moderate or severe cGVHD will be randomized 1:1 to itacitinib 200 mg QD plus corticosteroids or 300 mg QD plus corticosteroids.

[figure not shown]
Part 1 expansion is a Phase 2 with an initial safety run-in that will employ a randomized, open-label, parallel-cohort design to assess the safety and preliminary efficacy of itacitinib in combination with corticosteroids compared with corticosteroids monotherapy and select the appropriate dosing/schedule of itacitinib for Part 2 (Figure 2). A total of 140 participants (including those from Part 1) with moderate or severe cGVHD will be randomized 1:1 to 1 of 4 treatment groups that are itacitinib 300 mg QD plus corticosteroids (Treatment Group A), itacitinib 400 mg QD plus corticosteroids (Treatment Group B), itacitinib 300 mg BID plus corticosteroids (Treatment Group C) or corticosteroids monotherapy (Treatment Group D). Treatment Group C was discontinued as of Amendment 8. Randomization will be stratified by

cGVHD risk status (moderate vs severe). Treatment Groups B and C will have an initial safety run-in of 10 participants each to determine safety and tolerability of the dose before expanding.

Itacitinib treatment will continue until treatment failure (cGVHD progression, death, or initiation of new systemic cGVHD therapy), unacceptable toxicity, or withdrawal of consent and for a maximum of 36 months.

[figure not shown]
Part 2 will employ a randomized, double-blind, placebo-controlled design in order to assess the efficacy of itacitinib in combination with corticosteroids using the dose determined to be safe and tolerable in the Part 1 expansion (Figure 1 and Figure 2). Randomization will be stratified by cGVHD risk status (moderate vs severe). Participants randomized to the placebo group will be permitted to cross over to the experimental group after completion of the primary analysis as appropriate. All participants will be followed for survival after completion of study treatment.

Figure 1: Study Design Schema

Note: Treatment Group C discontinued as of SEP 2021.

Figure 2: Treatment Phase, Post-Treatment, and Survival Follow-Up

Adherence to the study design requirements, including those specified in the schedule of activities (Table 4), is essential and required for study conduct.

Table 4: Schedule of Activities

											Follow-Up)	
	Screening					Treatn	nent			Safety	GVHD ^a	Survival	
Visit Day (Range)	Day -28 to -1	D1	1	D14		D28/56/84/ 112/140/168			ЕОТ	Last Dose + 30 days	Q28D/ Q8W°	Q8W From EOT	Notes
Visit Window			±	3 da	ys		±	7 days		+ 5 days	± 7 days	± 14 days	
Administrative procedures	1				ı	1		T		1	r	T	T
Informed consent	X												
Inclusion/exclusion criteria	X												
Demography	X												
Relevant medical history	X												
Prior/concomitant medications	X					X			X	X			
Randomize using IVRS	X												
Contact IVRS/dispense study drug		X				X		X	X				
Administer study drug						X							Hold treatment on clinic visit days until blood draws complete
Administer corticosteroids						X							
Distribute reminder cards						X							
Monitor study drug compliance						X			X				
Monitor corticosteroid use						X			X				
Safety assessments													
AE assessments	X					X			X	X			
Physical exam/vitals/weight	X					X			X	X	X*		*Only weight
KPS	X					X			X	X			
Infection monitoring	X		X*						X*	X*			*As clinically indicated
Graft failure/chimerism*	X ^d					Х*			X*	X*	X*		*As clinically indicated
12-lead ECG	X								X				
Efficacy assessments	Т	1		1		1		T		Т	ı	Γ	T
cGVHD diagnosis and staging	Xe												
cGVHD response		Xf		X		X	X	X	X	Xa	Xa		

Table 4: Schedule of Activities (Continued)

											Follow-Up)		
	Screening					Treatm	ent			Safety	GVHD ^a	Survival		
Visit Day (Range)	Day -28 to -1	D1	D7	D14	D21	D28/56/84/ 112/140/168	D180	D196+ (Q28D/Q8W) ^b	ЕОТ	Last Dose + 30 days	Q28D/ Q8W°	Q8W From EOT	Notes	
Visit Window			Ⅎ	± 3 day	ys		± ′	7 days		+ 5 days	±7 days	± 14 days		
FEV1% (from PFTs)	X	Xg				X*	X	X**	X	X	X**		*Day 168 FEV1% may be omitted. **Q8W starting at Day 196 up to 1 year (ie, Days 252, 308, and 364) then Q16 weeks. Day 196 may be omitted.	
Disease/malignancy relapse	X							X*					*As clinically indicated.	
LSS		Xh				X	X	X	X				Part 2 only.	
QOL-SF-36 v2		Xh				X*	X	X**	X				Part 2 only.	
EQ-5D-3L		X^h				X*	X	X**	X				* Day 168 may be omitted.	
PGIC						X*	X	X**	X				**Day 196 may be omitted.	
PGIS		Xh				X*	X	X**	X					
New cGVHD therapy data												X		
Survival assessment												X		
Laboratory assessments														
Hematology	X	X^h	X	X	X	X	X	Q28D	X	X				
Serum chemistry	X	X ^h	X	X	X	X	X*	Q28D	X	X	X*		*Total bilirubin, ALT, and ALP. Direct and indirect bilirubin also required for participants with elevated total bilirubin.	
Lipid panel	X	X^h	X	X	X	X		X	X	X				
Serum pregnancy testing	X								X					
Serum or urine pregnancy testing						X		X						
Hepatitis screening	X													
HIV screening	X													
PK sampling (Part 1 and Part 1 expansion)		X	X			X							D1/7/28 only (predose, 1, 2, 5 h) *Treatment Group D in Part 1 expansion does not require PK sampling.	

Table 4: Schedule of Activities (Continued)

											Follow-Up	l	
	Screening					Treatm	ent			Safety	GVHD ^a	Survival	
Visit Day (Range)	Day -28 to -1	D1	D 7	D14	D21	D28/56/84/ 112/140/168	D180	D196+ (Q28D/Q8W) ^b	ЕОТ	Last Dose + 30 days	Q28D/ Q8W°	Q8W From EOT	Notes
Visit Window			±	3 day	ys	± 7 days				+ 5 days	±7 days	± 14 days	
PK sampling (Part 2)		X	X			Х							Participant 1-70: D1/7/28 (predose, 1, 2, 5 h). Participant 71-246: D7/28 (predose only).

VV-CLIN-000629 CONFIDENTIAL

^a Only for participants who completed itacitinib/placebo taper after an initial response (CR or PR) or discontinue early for reasons other than cGVHD disease progression and with no requirement for new cGVHD therapy (for a maximum of 24 months from Day 1).

b Every 28 days (± 7 days) up to 1 year (D364) from Day 1 and then every8 weeks (± 7 days), with the exception of hematology and serum chemistry, which will be performed every 28 days during the entire treatment period.

^c Every 28 days (± 7 days) up to 1 year (D364) from Day 1 and then every 8 weeks (± 7 days) up to 2 years from Day 1.

d Chimerism testing can be performed on Day 1 before study drug administration. Results are not required for randomization and treatment.

^e Chronic GVHD staging (see criteria in Appendix C) performed at screening will be used for eligibility assessment and stratification purposes

f Chronic GVHD organ score and overall severity score 0 to 10 (see criteria in Appendix E) will be performed on Day 1, and this will be the baseline for cGVHD response assessment during treatment and post-treatment follow-up.

g FEV1% performed within 7 days of Day 1 can be used for cGVHD response assessment if bronchiolitis obliterans was not diagnosed at screening.

h May be performed within 7 days of Day 1. If liver cGVHD is diagnosed at screening, total bilirubin, ALT, and ALP should be repeated on Day 1.

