- Itacitinib doses as high as 400 mg BID and 600 mg QD have been studied in other patient populations, for example, rheumatoid arthritis, plaque psoriasis, and myelofibrosis and were well-tolerated with manageable AEs (additional information can be found in the IB).

Considering the dose range and the corresponding safety profile across patients with acute and chronic GVHD and other autoimmune and oncology populations, doses of 400 mg QD and 300 mg BID were selected for further evaluation in an expansion to Part 1 of the

study (additional dose cohorts of 35 participants each). The original cohort of 300 mg QD will also be expanded to provide a more robust safety and efficacy assessment of this dose level; Part 1 expansion will also include 1 cohort of corticosteroids as single-agent for a contemporary comparison of the safety and efficacy of each combination cohort. Data from Part 1 expansion will guide dose selection for Part 2 of the study.

Itacitinib doses should be adjusted to maintain a consistent exposure with concomitant use of a strong CYP3A inhibitor; see Section 6.1.1.5 for more information.

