2.3.2.3. Preliminary Results for Part 1 Expansion

Preliminary data from the Part 1 expansion was reviewed ad hoc by an independent DMC. At the data cutoff date for the ad hoc DMC review (09 JUL 2021), 107 participants had been enrolled in the Part 1 expansion portion of the study in the 300 mg QD dose cohort (Treatment Group A; n = 32), 400 mg QD dose cohort (Treatment Group B; n = 25), 300 mg BID dose cohort (Treatment Group C; n = 24), and corticosteroid monotherapy dose cohort (Treatment Group D; n = 26). The median duration of exposure was 83 days (range: 2-579 days) across the itacitinib treatment groups. At the time of the data cutoff, 62 participants remained on treatment across the 4 treatment groups.

Malignancy relapse was the most frequent reason for discontinuation in Treatment Group C (itacitinib 300 mg BID in combination with corticosteroids). Although no interim analysis was planned, and the number of participants was small, with 4 confirmed relapses reported in this cohort versus 1 relapse in each of the 300 mg QD and 400 mg QD cohorts and no relapse in the corticosteroids alone cohort, the sponsor had decided, following the DMC recommendation, to discontinue the itacitinib 300 mg BID study arm.

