4. STUDY DESIGN

4.1. Overall Design

GRAVITAS-309 is a 2-part, multicenter Phase 2/3 study that will assess the efficacy and safety of itacitinib in combination with corticosteroids as first-line treatment for moderate or severe chronic GVHD.

4.1.1. Part 1

Part 1 is a run-in that will employ a randomized, open-label, parallel-cohort design with the primary objective to assess the safety and tolerability of itacitinib in combination with corticosteroids in order to identify the appropriate dose of itacitinib in combination with corticosteroids as initial treatment for moderate or severe cGVHD. A total of 20 participants with moderate or severe cGVHD will be randomized 1:1 to itacitinib 200 mg QD plus corticosteroids or 300 mg QD plus corticosteroids. Itacitinib treatment will continue until treatment failure (cGVHD progression, death, or initiation of new systemic cGVHD therapy), unacceptable toxicity, or withdrawal of consent. Participants will remain on study for a total of 37 months, including study treatment (up to 36 months), safety follow-up (30 days after EOT), and post-treatment GVHD follow-up (up to 24 months from Day 1), unless death or withdrawal of consent occurs earlier.

Chronic GVHD staging and grading will be assessed using NIH consensus guidelines (Lee et al 2015, Jagasia et al 2015); safety and tolerability will be assessed as per NCI CTCAE v4.03.

An analysis to determine the dose for further study will be performed once the 20th participant completes 28 days of study treatment. An external DMC will review data from this analysis and provide a recommendation on an appropriate dose for Part 2.

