3.1.2. Part 1 Expansion

A total of up to 140 participants (35 per treatment group) with moderate or severe cGVHD will be randomized 1:1 to 1 of 4 treatment groups: itacitinib 300 mg QD plus corticosteroids (Treatment Group A), itacitinib 400 mg QD plus corticosteroids (Treatment Group B), itacitinib 300 mg BID plus corticosteroids (Treatment Group C), or corticosteroids monotherapy (Treatment Group D).

Randomization will be stratified by cGVHD risk status (moderate vs severe). Treatment Groups B and C will have an initial safety run-in of 10 participants to determine safety and tolerability of the dose before expanding (see definition of DLT in Section 6.1.1.3 of the Protocol). Participants enrolled in the safety run-in will be monitored continuously using the Bayesian approach. Treatment Group C was discontinued as of Amendment 8, and participants in that treatment group who were ongoing were allowed to reduce to 400 mg QD plus corticosteroids.

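### Group A may include Part 1 participants who were never randomized against Groups B or D, and the SAP neither defines its membership nor separates them

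*Protocol*

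**What the plan says.** On who makes up the expansion:

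- Protocol Section 1, Table 3 counts "35 participants per group, including those from Part 1 meeting the criteria". The running text of Section 1 drops the qualifier: "A total of 140 participants (including those from Part 1". The available text does not define the criteria that Table 3 refers to.
- Protocol 2.3.2.2 adds: "The original cohort of 300 mg QD will also be expanded". It justifies Group D as "corticosteroids as single-agent for a contemporary comparison of the safety and efficacy of each combination cohort".
- Protocol 4.1.1 says that Part 1 participants are "randomized 1:1 to itacitinib 200 mg QD plus corticosteroids or 300 mg QD plus corticosteroids". Part 1 had no control arm.
- Protocol 4.1.2 and 10.1.2 and SAP 1, 3, 3.1.2, 3.3.2 and 5.2.2 describe the expansion without Part 1 participants. SAP 3.1.2 reads: "A total of up to 140 participants (35 per treatment group) with moderate or severe cGVHD will be randomized 1:1", to one of four groups.
- Protocol 2.3.2.3 gives enrolment at 09 JUL 2021 as "300 mg QD dose cohort (Treatment Group A; n = 32), 400 mg QD dose cohort (Treatment Group B; n = 25", with 24 in C and 26 in D. It adds: "The median duration of exposure was 83 days (range: 2-579 days) across the itacitinib treatment groups".

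On the analysis:

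- In SAP Table 4, ITT is everyone randomized, and Safety is grouped by treatment actually received. Neither is tied to a stage.
- SAP 7.1 uses the safety run-in population for Part 1 efficacy and the safety population for expansion efficacy. It does not place a participant who counts in both. SAP 6.2 uses a Part 1 expansion population that Table 4 does not define.
- SAP 7.3.1 compares A, B and D, with exploratory CMH tests at Month 6 for A versus D and B versus D. SAP 3.3.2 allows the posterior to inform the Part 2 dose. SAP 7.2 bases dose selection mainly on adverse events. SAP 3.2 plans no formal test.
- In Appendix A, several baseline tables come in two stage versions, but response tables 2.2.x and AE tables 3.2.x have no stage label.

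**The concern.** Group D was added so that each combination cohort would have a contemporary control. If Group A contains Part 1 participants, part of A versus D and A versus B is neither concurrent nor randomized. Two programmers could follow this SAP and produce different Group A denominators.

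The amendment history shows that the stages differ in ways that could affect toxicity. Amendment 6 (16 DEC 2019) added posaconazole to the drugs that require an itacitinib dose reduction. Amendment 7 (03 APR 2020) changed Inclusion Criterion 5 to make the assessment of hematologic toxicity more accurate. Dose selection rests mainly on adverse events, so mixing stages in Group A could affect the comparison that guides the Part 2 dose.

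**Working it through.** **1. Stated total (Protocol Table 3).** Part 1 has 20, the expansion 140 and Part 2 246. With no overlap, 20 + 140 + 246 = 406. The stated total is about 401, and 406 − 401 = 5, so an overlap of 5 gives it exactly. An overlap of 10 gives 396. All these figures are approximate, so totals of 406 and 396 are also compatible with 401. Using the 21 actually enrolled in Part 1 (Protocol 2.3.2.1), the same subtraction gives 6. The total does not settle the number.

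**2. Where carried-over participants would go.** Part 1 used 200 and 300 mg QD. The expansion used 300 mg QD, 400 mg QD, 300 mg BID and corticosteroids alone. Only 300 mg QD is shared. The Part 1 300 mg QD cohort had 10 participants, which caps the number at 10.

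**3. Exposure dates (Protocol 2.3.2.3).** Duration = last dose − first dose + 1. An exposure of 579 days at 09 JUL 2021 needs a first dose by 09 JUL 2021 − 578 days = 09 DEC 2019. That is 116 days before Amendment 7 (03 APR 2020) created the expansion. A participant starting on the amendment date could reach at most 463 days.

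**4. Enrolment at the cutoff.** 32 + 25 + 24 + 26 = 107. The mean of B, C and D is 75/3 = 25.0, so A has 7 more. Under simple equal allocation, P(A ≥ 32 of 107) = 0.145. This fits carry-over but does not show it.

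**5. Share of Group A and shift in its rate.** Let k be the number carried over and d the assumed difference in response between Part 1 and concurrent 300 mg QD participants, in either direction. Shift = (k/35) × d.

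| k | share of 35 | d = 10 points | d = 20 points |
|---|---|---|---|
| 5 | 14.3% | 1.4 | 2.9 |
| 10 | 28.6% | 2.9 | 5.7 |

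The documents give no Part 1 response rate, so d is an assumption.

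**6. Effect on the posterior (Protocol Table 23, SAP Table 3).** The prior values and the margin are not shown. P(pA − pD > δ), with independent Beta(1 + s, 1 + n − s) posteriors and δ = 0.15, reproduces all 30 cells within 0.05 points, so both are inferred. A shift of 2.9 or 5.7 points in 35 is 1 or 2 responders. From 28 versus 20 (73.9%), losing 1 or 2 responders in A gives 64.7% or 54.9%. Gaining 1 or 2 gives 81.9% or 88.4%.

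**7. Cost of a concurrent Group A.** If Group A totals 35, the concurrent part is 35 − 5 = 30 or 35 − 10 = 25. The SE ratio for A − D is √(1/n + 1/35) / √(2/35): 1.041 at n = 30 and 1.095 at n = 25. At 80% response in A against 20/35 in D, the posterior is 73.9% for 28/35, 72.6% for 24/30 and 70.9% for 20/25. Losing sample size matters little here; a difference between the stages could matter more.

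**The case against.** Extending the 300 mg QD cohort is declared openly in the Protocol, so pooling is a stated design choice in a descriptive stage. That is fair, and it is why the pooled result should stay. It does not say who is pooled, and it does not make pooled participants concurrent with Group D.

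A reader might infer that the SAP contradicts the Protocol. It does not: Protocol 4.1.2 and 10.1.2 are equally silent. The gap lies between the Protocol summary with 2.3.2.2 and the Protocol body, whose text the SAP follows.

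The evidence for carry-over is indirect. The exposure range has no stated denominator, the enrolment imbalance could be chance, and the total is approximate. The design figures are not reproduced in the available text and could show the carry-over or define the criteria. These limits stand. They leave the number open, and the membership rule is still missing from the SAP's own definitions.

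The assumed 10 to 20 points have no source in the documents. That also stands, and the shifts above illustrate sensitivity only.

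A reader might also take B versus D as a fully concurrent benchmark. The documents do not show this: Group B had a 10-participant safety run-in, and they do not say how A and D enrolled meanwhile.

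**Conclusion.** The point holds as an unreconciled definition of Group A with a possible effect on dose-selection comparisons. Carry-over into Group A is a strong inference from the shared dose, the stated intent and the 579-day exposure. The last assumes that no one was randomized into the expansion before Amendment 7 and that the exposure range describes the expansion's itacitinib groups. The number is not stated: 5 if 401 is exact, and 10 at most if the Part 1 300 mg QD cohort was 10.

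As written, the SAP allows those participants into A versus D (response rates, the exploratory CMH test and the posterior) and into the descriptive A-versus-B comparison. The SAP names no A-versus-B test.

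A reader might infer that the dose comparison is biased, or that it favours itacitinib. The documents support neither: size and direction are unknown. No formal test and no Part 2 inference is affected.

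**What to change.** 1. Reconcile Protocol Section 1, Table 3 and 2.3.2.2 with Protocol 4.1.2 and 10.1.2 and the SAP sections listed above.
2. In SAP 5.2.2, state which and how many Part 1 participants are in Group A, and what the criteria in Table 3 are.
3. For Month 3 and Month 6 response, the A-versus-D CMH test, the posterior and the main AE summaries, report A against D and B using only participants randomized under the Part 1 expansion schedule. Include those randomized after Group C closed; a rule tied to a four-group list could drop them although they are concurrent. Compute the posterior at the actual group sizes.
4. Show the pooled Group A result, labelled as such, beside each of these.
5. Add stage labels to Tables 2.2.x and 3.2.x.

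The cost is wording, labels, a recomputed posterior and an extra presentation of the key tables. No data are lost. The concurrent Group A would be about 25 to 30, which makes the SE of A − D about 4% to 10% larger.
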